#### Subject Withdrawal or Discontinuation

Subjects maintain the right to discontinue their participation in the study at any point without penalty or loss of benefit to which the subject is otherwise entitled per ICH E6 4.8.10(m) guidelines. Although, a subject is not obliged to give his or her reason(s) for withdrawing prematurely from this study, the investigator should make a reasonable effort to ascertain the reason(s), while fully respecting the subject's rights per ICH E6 4.3.4 guidelines.

## **Device** Failure

Subjects will be considered a treatment failure, and will be withdrawn from the study if any sections of the device (tibial or talar metal components) have been removed at any time during their participation. This should be reported onto the adverse event form. In addition, any surgical intervention during study participation that relates to their total ankle replacement will be reported on the surgical intervention case report form.

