**ISO 14155:2011** also specifies general requirements intended to protect the rights, safety and well-being of human subjects, ensure the scientific conduct of the clinical investigation and the credibility of the results, define the responsibilities of the sponsor and principal investigator, and assist sponsors, investigators, ethics committees, regulatory authorities and other bodies involved in the conformity assessment of medical devices.

Osteolysis - pathological destruction or disappearance of bone tissue.

Subsidence- sinking or settling in bone, as of a prosthetic component of a total joint implant.

Study Title	The INFINITY ™ Total Ankle Replacement Follow-up (ITAR)					
Study Design	Prospective, multi-site, multi-year post-market clinical follow-up study					
Study Group	Primary/Unilateral and/or bilateral Total Ankle Arthroplasty subjects implanted with INFINITY TM Total Ankle System					
N Subjects	200 with 10 sites					
Follow-Up Schedule	Subject enrollment will consist of a Pre-operative, Operative, 6 months, 1 yr., 2 yr., 5yr., 7 yr., 10 yr., and an unscheduled visit as needed.					
Primary Objective	Evaluate the long-term survivorship of the INFINITY ™ implant over 10 years					
Secondary Objective(s)	
 
Secondary objectives assessed will be to:
 
Identify and assess the implant for component loosening and/or subsidence, any osteolysis and/or cyst formation through radiographic evaluation early and throughout the lifetime of the implant.
 
Compare the improvements in self-reported physical, mental, and social health measures from pre-op through 10 years post operatively; assessed by PROMIS® Global Health.
 
Compare pain and functional improvement in the Ankle Osteoarthritis Score (AOS), which is a visual analogue scale specifically designed as a modification of the Foot Function Index.
 
Compare the improvement in patient/physician reported function scores from pre-op through 10 years post-operatively, assessed by the FAOS questionnaire.
 
Compare satisfaction of total ankle replacement post operatively utilizing a four point scale
 
Identify and report the safety of the implant in terms of complications and adverse events.
 
					

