Inclusion Criteria	
 
Subjects to be included in the study must meet all of the following criteria:
 
Be 21 years of age or older at the time of surgery;
 
Diagnosed with unilateral and/or bilateral ankle joint disease;
 
Diagnosed with ankle joint damage from rheumatoid arthritis, post-traumatic, or degenerative arthritis;
 
Willing and able to consent to participate (written, informed consent;
 
Willing and able to attend the requested follow-up visits;
 
A clinical decision has been made to use INFINITY™ Total Ankle System replacement prior to enrollment in the research.
 
					
Exclusion Criteria	
 
Subjects will be excluded from the study if they meet any of the following criteria:
 
Subjects with an ankle condition, as determined by the investigator, to be an inappropriate candidate for a total ankle replacement;
 
Subjects requiring revision total ankle replacement of the ankle being considered for study
 
					

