#### **Point of Enrollment**

Subjects will be considered enrolled in the study when they have:

- Been informed of all aspects of the study and have signed Informed Consent document
- Acknowledged the appropriate patient data release information (included in the Informed Consent document)
- Satisfied the Inclusion/Exclusion Criteria
- Implanted with the Device

Investigators should document subject enrollment by completing the screening and enrollment logs located within the trial master file. The Source documentation should clearly state that all inclusion and exclusion criteria have been met and the patient data release and informed consent documents have been signed and appropriately dated prior to any study related activity,

The investigative sites will be assigned three digit a site code **\*\*\***, and at enrollment the subject will be assigned a sequential subject identification number corresponding to the order the subject was enrolled (i.e. the first subject enrolled at each site will be site number **\*\*\*** followed by subject identifier 001). The assigned codes will be used to identify the subject on all case report forms. All investigative sites will be provided protocol training of the during the site initiation visits. Investigative sites will be provided paper case report forms/booklets, which may be used as source documentation, these must signed by the individual completing the form; i.e., coordinator, patient, or investigator.

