## Effectiveness objectives

The primary effectiveness objective is to evaluate the long-term survivorship of the INFINITY® implant and improvement in patient function and quality of life. Survivorship will be measured by the length of time until implant failure.

Improvement in subject function and quality of life was assessed using the PROMIS Global Health, Ankle Osteoarthritis Score (AOS) and FAOS Questionnaire.

In addition, the level of patient satisfaction of their total ankle replacement was assessed at each post-operative visit.

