### Survivorship of INFINITY® Total Ankle System

Survivorship of INFINITY® Total Ankle System will be based on secondary surgical intervention performed on the original implant. The Kaplan Meier survivorship method and life table analysis will be employed. Time to surgical intervention due to implant failure will be the survivorship endpoint of INFINITY® Total Ankle System. In addition, time to reoperation to exchange or remove any part of the INFINITY® Total Ankle System or surgical intervention due to failure of the implant as survivorship endpoint will also be analyzed. Subjects who did not undergo revision or reoperation due to implant failure at the time of reporting will be censored at the last follow-up. The Kaplan Meier survival curve with the 95% Confidence Interval will be constructed.

Year since	Number	Number of	Lost	Survival	95%
implantation	at start	failed implant		Rate	Confidence
					Interval
0-1	1		I		
1-2					
2-3					
3-4					
4-5					
5-6					
6-7					
7-8					
8-9					
9-10					

Table . Kaplan-Meier life-table survival of INFINITY® Total Ankle System.

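### If a subject has two study ankles, the per-subject withdrawal rule ends follow-up of the intact implant, and the survivorship table does not fix its unit of analysis

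*Protocol*

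**What the plan says.** - **Who enters.** The study group in both synopses is "Primary/Unilateral and/or bilateral Total Ankle Arthroplasty subjects implanted with INFINITY" devices, and an inclusion criterion reads "Diagnosed with unilateral and/or bilateral ankle joint disease". The first of these describes the operation, not only the disease.
- **Unit of enrolment.** Protocol, Point of Enrollment: "at enrollment the subject will be assigned a sequential subject identification number corresponding to the order the subject was enrolled". No identifier for the ankle is described.
- **Unit of failure and withdrawal.** Protocol, Device Failure: "Subjects will be considered a treatment failure, and will be withdrawn from the study if any sections of the device", where the trigger is that "tibial or talar metal components) have been removed at any time during their participation". No side is named.
- **Unit of the endpoint.** SAP, Effectiveness objectives: "Survivorship will be measured by the length of time until implant failure".
- **Unit of censoring.** SAP, Survivorship of INFINITY Total Ankle System: "Subjects who did not undergo revision or reoperation due to implant failure at the time of reporting will be censored at the last follow-up". The life table in the same section has a column for failed implants, while the *Number at start* and *Lost* columns carry no unit.
- **Unit of inclusion.** SAP, Report Timing of survivorship assessment, selects patients: those with scores at eight or more years for the final analysis, plus those who were reoperated or revised.

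**The concern.** The primary objective is survivorship of the implant, but follow-up is governed by what happens to the person. Suppose a subject has a study implant in each ankle. Removal of a metal component on one side takes the subject out of the study, so the intact implant on the other side stops contributing at that moment. That implant has not failed; it is lost because its partner did.

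The analysis section then leaves the denominator open. Failed implants are counted, subjects are censored and patients are selected. Two analysts could follow the same text and report a per-implant rate or a per-subject rate. For staged operations the plan does not say which surgery date starts the clock. For a bilateral subject withdrawn early after one failure, it does not say whether the intact ankle is kept, censored or excluded under the eight-year rule. No variance method allows for two ankles in one subject.

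At stake are the meaning of the primary rate, some implant follow-up and the width of its confidence interval.

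**Working it through.** **1. Is there a figure to reproduce?** No. The protocol says the sample size has no statistical basis. Neither document gives a bilateral share, a survival rate or a within-subject correlation. The SAP gives 155 patients and no count of implants. Everything below except 155 is an assumption, used for scale.

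**2. Intact implants that lose follow-up.** Assume 5–15% bilateral subjects, 10% failure per implant at ten years, and independent ankles.
- Bilateral subjects: 0.05 × 155 ≈ 8; 0.15 × 155 ≈ 23.
- Probability that exactly one of two ankles fails: 2 × 0.1 × 0.9 = 0.18.
- Intact implants affected: 8 × 0.18 = 1.4; 23 × 0.18 = 4.1. So about 1 to 4.

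**3. Change of estimand.** Same assumptions.
- Survival to first failure in a bilateral subject: 0.9² = 0.81.
- Overall at 5%: 0.95 × 0.90 + 0.05 × 0.81 = 0.8955, or 89.6%.
- Overall at 15%: 0.85 × 0.90 + 0.15 × 0.81 = 0.8865, or 88.7%.
- Per implant the rate is 90% throughout.

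**4. Bias from the withdrawal rule.** Paired failure times were simulated with exponential margins and a Gaussian copula (400,000 subjects, no other loss to follow-up). The grid was bilateral share 5, 10 and 20%; ten-year implant survival 80, 90 and 95%; copula correlation 0, 0.3 and 0.6. Selected ten-year results, in %:

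| Survival | Bilateral share | Correlation | KM, both ankles followed | KM, intact ankle censored at partner's failure | First failure per subject | Failed implants over subjects |
|---|---|---|---|---|---|---|
| 90 | 5 | 0.3 | 90.0 | 90.0 | 89.6 | 89.5 |
| 90 | 10 | 0.6 | 90.0 | 90.3 | 89.4 | 89.0 |
| 90 | 20 | 0.6 | 90.0 | 90.5 | 88.7 | 87.9 |
| 80 | 20 | 0 | 80.1 | 80.0 | 76.9 | 76.1 |
| 80 | 20 | 0.6 | 80.0 | 81.2 | 78.0 | 76.0 |

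The withdrawal rule moves the implant-level estimate by 0 to about +1.2 points. With correlation 0 there is no shift beyond simulation noise. The choice of unit moves the estimate by about 0.1 to 4 points over the grid. The 4-point end is the last column, which counts failures as if both ankles stayed under observation.

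**5. Precision and clustering.**
- Half-width of the 95% interval at 90% survival, n = 155, no censoring: 1.96 × √(0.9 × 0.1 / 155) = 4.7 points. At 80% it is 6.3 and at 95% it is 3.4.
- Follow-up lost at 90% survival, 10% bilateral, independent ankles: at most 15.4 implant-years out of 155 × 1.10 × 10 = 1,705, or 0.9%.
- Design effect from two ankles in one subject: 1.06 at 90% survival, 10% bilateral and correlation 0.6; largest in the grid 1.12. Since √1.12 = 1.06, the interval widens by about 6% at most.

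**The case against.** **One index ankle may have been intended.** The exclusion criterion on revision speaks of a single candidate ankle. The protocol's medical history form records a contralateral replacement as the status of another joint. The operative form asks for one operation date and previous surgery to the index joint, and the SAP describes one surgery day. This stands as a limit on the point: the documents permit two study ankles but do not say that any subject has them. It does not remove the point, because no sentence states a one-ankle rule and both synopses name bilateral arthroplasty.

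**A reader might infer that the withdrawal rule is informative censoring that biases the primary rate.** The documents do not support that without qualification. If a subject's two ankles fail independently, censoring one at the other's failure is non-informative. Correlation is plausible, since both ankles share patient factors, but no figure is given.

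**A reader might take the move from 90% to 89.6% or 88.7% as the damage done by withdrawal.** It is not. It compares two estimands, survival per implant and survival to first failure per subject.

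**A reader might infer that a bilateral subject routinely adds two failures to one unit at risk.** After a metal-component removal the subject is withdrawn, so a later second failure would not be seen. Two failures need simultaneous events, or a first event without metal removal, such as an insert exchange, which the SAP's additional endpoint on exchange or removal of any part would count. *Number at start* can also be read as implants, so a numerical error is possible but not shown.

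**No stated decision turns on it.** The study is single-arm, with no survivorship test or performance goal. That limits the importance of the point but does not supply the missing unit.

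**Conclusion.** The point holds conditionally. As written, the withdrawal rule ends observation of an intact study implant whenever a subject has two and one loses a metal component, and the survivorship section does not settle whether it counts ankles or people.

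If no subject has two study ankles, the effect is nil. With independent ankles the cost is precision alone: about 1 to 4 implants at an assumed 5–15% bilateral share and 10% failure. With correlated failures the ten-year implant estimate rises by up to about 1.2 points, and that extreme needs 20% bilateral, 80% survival and correlation 0.6. At 90% survival the largest shift in the grid is 0.5 points. The choice of unit usually matters more than the withdrawal rule. Neither effect exceeds the sampling half-width at the same survival rate. The reason to act is that the primary rate lacks a defined unit and the repair is cheap, not that a large error has been shown.

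**What to change.** 1. **Protocol, Device Failure, and SAP, Survivorship:** state whether one or both ankles of a subject may enter the study. If only one, say so and name it the index ankle; the withdrawal problem then disappears.
2. **If both may enter, Protocol, Device Failure:** let failure end study follow-up for the failed ankle only, with the subject staying in study follow-up for the other study implant. This concerns data collection, not treatment.
3. **SAP, Survivorship and Report Timing of survivorship assessment:** make the implanted ankle the unit, timed from its own surgery date. Count number at start, failed and lost all in ankles. Apply the inclusion rule by ankle, and say how an intact ankle is handled after its partner fails.
4. **Interval:** use a variance clustered on subject, and add a sensitivity analysis restricted to each subject's first study ankle.

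The cost is a protocol amendment and SAP wording. The protocol's operative form already collects the date of operation, and the SAP's baseline section lists the ankle to be treated. A few subjects would have longer study follow-up and the interval may be slightly wider. Enrolment is closed, so follow-up of subjects already withdrawn may not be recoverable.

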#### **Procedures and Case Report Forms**

Subject medical history and demographic information will be collected and recorded onto the demographic case

report form. The following information will be collected on these forms:

- Date of birth
- Gender
- Height
- Weight
- BMI calculation
- Smoking status
- Status of other joints that affect ambulation (i.e., knee replacement, contralateral arthritis and/or ankle replacement)
- Concomitant health conditions (diabetes and other medical conditions, etc.)

#### **Operative Procedure Information**

The information related to the subject's operation will be collected and recorded according to the Operative

Information Case Report Forms. The following operative information related to the primary TAR procedure will be

documented on these forms:

- Primary diagnosis
- Any previous surgery to index joint
- Date of operation
- Site location

- Surgical approach
  - Instrumentation type (standard) or (additional approved INFINITYTM instrumentation)
  - List concomitant operative procedures such as tendon/deltoid lengthening or other reconstructive process required to make final implantation correct
- Cement use
- Intraoperative complications (to be collected on the Adverse Event Case Report Form)
- Product description and eight-digit product code for all components implanted

## Patient Reported Outcome Measures (PROMS)

The standard care pathway for patients undergoing Total Ankle Replacement includes the collection of Patient Reported Outcome Measures (PROMS), in some institutions. The study aims to use this data, wherever possible, to fulfill the secondary outcome measures of the study and avoid duplication of data collection. As there is some variance nationally regarding the questionnaires which are used for PROMS data collection, participants may be required to supplement one or more of the following questionnaires for the purposes of the research study:

*PROMIS*® (*Patient-Reported Outcomes Measurement Information System*) is a set of person-centered measures that evaluates and monitors physical, mental, and social health in adults and children. It can be used with the general population and with individuals living with chronic conditions.

• PROMIS Scale v1.2 - Global Health

*The Foot and Ankle Outcome Score (FAOS)* is a self-report measure that evaluates symptoms and functional limitations in individuals with generalized foot and ankle disorders. Items for the Foot and Ankle Outcome Score were adapted from the Knee Injury and Osteoarthritis Outcome Score. The FAOS is composed of the following 5 subscales: pain (9 items), other symptoms (7 items), activities of daily living (7 items), sports and recreational activities (5 items), and foot and ankle-related quality of life (4 items).

*Ankle Osteoarthritis Score (AOS)* is a reliable, validated, visual analog based, disease specific self-administered instrument designed specifically to measure disability and pain from ankle osteoarthritis. Both Pain and Disability components are used to calculate the total score. The score is from zero to one hundred with a lower score indicating more normal function. The minimally important difference for the AOS score is not known.

*Total Ankle Replacement Satisfaction*, this study will be evaluating the patient's satisfaction with their total ankle replacement post operatively (6months,1yr,2yrs,5yrs,7yrs,10yrs) utilizing a four point scale.

## Surgeon-completed Radiographic Report

This report includes usual standard of care pre-operative radiographs will include a standing AP and lateral film of

the ankle. Arthritis can be assessed by CT if available but, not required for this study.

Coronal plane deformity should be measured in degrees as the angle between a line perpendicular to the anatomical axis of the tibia and a line drawn along the top of the talar dome see (see figure) and recorded as either varus or valgus.

The Canadian Orthopaedic Foot and Ankle Society (COFAS) end-stage arthritis classification should be identified and recorded as:

## Type 1: Isolated ankle arthritis

Type 2: Ankle arthritis with intra-articular varus or valgus deformity or a tight heel cord, or both

- intra-articular ankle varus or valgus alignment\* was defined as the angle of the proximal talar surface (talar tilt) to the lateral border of
- the tibia in the distal diaphysis and metaphyseal region more than 10 degrees on the AP weightbearing ankle views

Type 3: Ankle arthritis with hindfoot deformity, tibial malunion, midfoot abductus or adductus, supinated midfoot, plantar flexed first ray, etc.

- hindfoot deformity defined as the angle between the lateral border of the calcaneus and the long axis of the tibia on the AP view of the ankle (varus more than 5 degrees, valgus more than 10 degrees)
- Tibial deformity defined as an angulation between the lateral border of the tibia more than 10 degrees on the AP view of the ankle\*\*

Type 4: Types 1, 2, and 3 plus subtalar, calcaneocuboid, or talonavicular arthritis\*\*\*

The post-operative radiographic evaluations will be to assess, record, and report migration, loosening, subsidence of the device, any osteolysis and cyst formation.

\* Greater than 10 degrees (defined as the angle between a line perpendicular to the anatomical axis of the tibia and a line drawn along the top of the talar dome see (see figure) and recorded as either varus or valgus)

\*\* If the patient has required staged surgical correction of deformity as part of the management of ankle arthritis (within 18 months of TAR), this should be considered a type 3. However, if the patient has undergone historic corrective surgery then the current foot position should be used for the purpose of COFAS grading (ie if fully corrected then can be Grade 1).

\*\*\* this would include patients with prior arthrodesis of the subtalar, calcaneocuboid, or talonavicular joints

# STATISTICAL CONSIDERATION

#### Sample Size

The total sample size is 200 subjects. The sample size was not calculated using statistical methods. A nonparametric statistical analysis for survivorship using the Kaplan-Meier will be applied to determine the implant survivorship.

Mechanical survivorship for total hip and knee replacement is currently thought to be approximately 10 years. This benchmark for long-term data collection is not only relevant to the safety and survivorship of the implant but, also to provide assurances that for the introduction of new implants, a data collection plan is in place for ongoing evaluations and reporting.

The information gained from this data collection will be analyzed at times based on potential publication periods around 2, 5, and 7 years with a final analysis after all subjects haven completed all follow-up requirements at the 10 year final visit. In addition, at time points determined by the investigators and/or Wright Medical will be evaluated as needed or required for additional analysis of data for reporting and/or publication purposes will be done throughout the study.

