## Primary and Secondary Endpoints

The primary endpoint is a survivorship rate at 10 years as defined with a Kaplan Meier survivorship analysis. Secondary endpoints identify, assess and compare functional improvements or deviations collected through investigator observation and patient self-reporting, and include:

• Identification and assessment of the implant through radiographic assessment for component loosening and/or subsidence, any osteolysis and/or cyst formation early and throughout the lifetime of the implant.

- Comparison of improvements in self-reported physical, mental, and social health measures from pre-op through 10 years post operatively; assessed by PROMIS®.
- Comparison of pain and functional improvement from pre-op through 10 years in the AOS which is a visual analogue scale specifically designed as a modification of the Foot function Index.
- Comparison of the improvements in patient/physician reported function scores from pre-op through 10 years post-operatively, assessed by FAOS scores.
- Compare satisfaction of total ankle replacement post operatively utilizing a four point scale
- Identification and reporting on the safety of the implant in terms of complications and adverse events.

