### **Other considerations**

### 1. Outcome Measures Report Timing

All analyses of outcome, except survivorship, will be done at each post-surgery visit namely: at 6 months, 1, 2, 3, 5, 7 years. The final analysis at 10 years will be done after all the subjects have completed final visit. In addition, at time points determined by the investigators and/or Wright Medical will be evaluated as needed or required for additional analysis of data for reporting and/or publication purposes will be done throughout the study.

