### 2. Report Timing of survivorship assessment

There will be two timepoints to assess and report survivorship, at the 5th (intermediate survivorship assessment) and 10th (long-term survivorship assessment) year follow-up.

At the intermediate assessment of survivorship (5th year follow-up), only patients with follow-up scores obtained at least four years after surgery will be included in the analysis. Patients who underwent reoperation or revision surgery with in four years of surgery will not be excluded. At the final assessment of survivorship (10th year follow-up), only patients with follow-up scores obtained at least eight years after surgery will be included in the analysis. Patients who underwent reoperation or revision surgery will be included in the analysis. Patients who underwent reoperation or revision surgery will be included in the analysis.

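### The Protocol plans analyses around years 2, 5 and 7 plus a final one, but the SAP schedules survivorship, the primary outcome, only at years 5 and 10, so the 2- and 7-year reports have no planned Kaplan-Meier estimate

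*Protocol*

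**What the plan says.** **Protocol.** Primary and Secondary Endpoints states: "The primary endpoint is a survivorship rate at 10 years as defined with a Kaplan Meier survivorship analysis". Under Statistical Consideration, Sample Size names Kaplan-Meier as the survivorship method. Two paragraphs later it says the collected information "will be analyzed at times based on potential publication periods around 2, 5, and 7 years with a final analysis" once all subjects have finished the 10-year visit. It also allows further analyses when the investigators or the sponsor want them. Device Failure says subjects "will be withdrawn from the study if any sections of the device (tibial or talar metal components) have been removed".

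**SAP.** Under Other considerations, item 1 reads: "All analyses of outcome, except survivorship, will be done at each post-surgery visit namely: at 6 months, 1, 2, 3, 5, 7 years", with the final analysis at 10 years. Item 2 reads: "There will be two timepoints to assess and report survivorship, at the 5th (intermediate survivorship assessment) and 10th (long-term survivorship assessment) year follow-up". Item 2 then limits the 5-year analysis to patients with scores at least four years after surgery, and the 10-year analysis to those with scores at least eight years after, while keeping patients who were reoperated or revised. The Survivorship section instead censors unrevised subjects at last follow-up and provides a life table in one-year intervals from 0-1 to 9-10. Missing Data rules out imputation and excludes patients who lack the data an analysis needs.

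**The concern.** The Protocol's analysis times cover the collected information as a whole. The SAP makes one exception, for the primary outcome, and gives no reason. Because subjects leave the study when a tibial or talar metal component is removed, and missing scores are not imputed, the scores at years 2 and 7 describe subjects whose metal components remain. The natural companion to such scores is an estimate of how many implants are no longer in place, with its uncertainty. The Protocol ties these time points to possible publication, and its Introduction says little has been published on this device. A reader of the 2- or 7-year report would thus see results among retained implants without a survivorship estimate beside them.

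**Working it through.** No figure in the plan needs reproducing: the Protocol says its sample size was not calculated, and neither document gives an expected failure rate. The check compares schedules and then sizes the gap under stated assumptions.

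**1. Schedules (years)**

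| Source | Times |
|---|---|
| Protocol, Sample Size | 2, 5, 7, 10 |
| SAP item 1, outcomes other than survivorship | 0.5, 1, 2, 3, 5, 7, 10 |
| SAP item 2, survivorship | 5, 10 |

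Protocol times without survivorship: {2, 5, 7, 10} minus {5, 10} = {2, 7}. All other outcomes are scheduled at both. Two of the four Protocol analyses carry survivorship.

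**2. Length of the delay.** The yearly life table shows year-2 survival in the 5-year report (5 - 2 = 3 years later) and year-7 survival in the final report (10 - 7 = 3 years later). With the planned 24-month recruitment, complete reports would fall at 2 + 2 = 4, 2 + 5 = 7, 2 + 7 = 9 and 2 + 10 = 12 years after the first subject. The actual recruitment period is not given, and enrollment closed at 155 instead of 200.

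**3. Failures involved.** Assumptions: constant hazard, all 155 followed, and a proportion F failed by year 10 of 5%, 10% or 20%. The proportion failed by year t is 1 - (1 - F)^(t/10).

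| F | Year 2 | Year 5 | Year 7 | New, years 5-7 |
|---|---|---|---|---|
| 5% | 1.0% = 1.6 | 2.5% = 3.9 | 3.5% = 5.5 | 1.5 |
| 10% | 2.1% = 3.2 | 5.1% = 7.9 | 7.1% = 11.0 | 3.1 |
| 20% | 4.4% = 6.8 | 10.6% = 16.4 | 14.5% = 22.4 | 6.1 |

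Of the 11 failures assumed by year 7, about 8 would already be in the 5-year survivorship report.

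**4. Effect on the scores.** If failed subjects would have scored 20 points worse on a 0-100 scale (assumed), the mean among retained implants is too favourable by 20 times the failed proportion. At year 2 that is 20 x 0.021 = 0.4 points (0.2-0.9). At year 7 it is 20 x 0.071 = 1.4 points (0.7-2.9). This takes every failure as a metal-component removal; an insert exchange alone does not trigger withdrawal, so the true effect could be smaller.

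**5. Would an early estimate be informative?** With complete follow-up, Greenwood gives SE = sqrt(S(1 - S)/n), and the log-log 95% limits are S^exp(±1.96 SE/(S|ln S|)). With n = 155:

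- S = 98%: 94.0-99.3%
- S = 95%: 90.1-97.5%
- S = 90%: 84.1-93.8%; with 20% loss (n = 124), 83.2-94.1%

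These intervals are usable for description.

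**The case against.** The strongest reply is that no firm commitment is broken. A reader might infer that the Protocol promised survivorship at years 2 and 7 and that the SAP withdrew it. The text does not go that far. The Protocol says only that "The information gained from this data collection will be analyzed at times" linked to possible publication; Kaplan-Meier is named earlier in the section with no time attached. The stated aim of ongoing evaluation and reporting is general and not specific to survivorship. Both documents allow extra analyses on request, so a 2- or 7-year estimate is unscheduled, not barred. This stands, but discretion over when to show failure estimates is weaker than a fixed schedule, and the SAP does not explain its exception.

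A reader might also infer that failures are hidden in these reports. They are not. The SAP plans cumulative adverse event rates, secondary interventions by type (including component removal) and by reason (including implant failure), and follow-up counts at each visit. Table 3.2 is titled as surgical interventions by visit, although the SAP gives no shell showing its contents. With about 3 failures by year 2, a crude proportion would differ little from Kaplan-Meier unless early loss were heavy. What is missing is narrower: a planned survivorship estimate with its confidence interval.

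The later life table is only a partial answer. Under item 2's restrictions, it would drop unrevised subjects with shorter follow-up while keeping the failures, so it would not be an estimate for all implanted subjects.

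**Conclusion.** The point holds in a limited form. The two schedules differ at exactly years 2 and 7, and the outcome left out is the primary one. The consequence is a three-year delay in a descriptive estimate, in reports whose scores come from subjects with metal components in place.

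Under a constant failure rate with 10% failed by year 10 (range 5-20%), about 3 of 155 failures (2-7) precede the 2-year report. About 3 new ones (1.5-6) fall between the 5- and 7-year reports. It would be wrong to describe all 11 assumed year-7 failures as lacking an estimate, or to say that the 10-year primary result is compromised by this timing gap. The failure rates are assumptions, since the documents give none. The mismatch itself rests on no assumption. It merits correction mainly because correction is cheap and these reports may be published.

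**What to change.** Make three edits under Other considerations in the SAP.

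1. Item 1: replace the bare exception with *except survivorship, which is timed as in section 2*. Deleting the exception outright would also schedule survivorship at 6 months, 1 year and 3 years.
2. Item 2: replace the two-timepoint sentence with *Kaplan-Meier survivorship with 95% CI and number at risk is reported at the 2-, 5-, 7- and 10-year analyses for all implanted subjects, censored at last follow-up as in the survivorship section; the 10-year estimate is the primary result and earlier estimates are descriptive.*
3. Item 2: delete the sentences restricting the analysis to patients with scores at least four or eight years after surgery. They conflict with the censoring rule in the Survivorship section and with the new text.

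The cost is SAP wording and two more runs of a planned analysis, with few events at year 2. No hypothesis test is attached, so no error rate changes. The third edit also changes who enters the 5- and 10-year analyses, so it should be made deliberately and recorded as such. If the sponsor prefers to keep survivorship at years 5 and 10, the lesser remedy is to amend the Protocol's schedule and give the reason.
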